## 1 INTRODUCTION

This statistical analysis plan (SAP) describes the statistical methods to be used during the reporting and analyses of data collected under Aerpio Therapeutic, Inc. Protocol AKB-9778-CI-5001.

This SAP should be read in conjunction with the study protocol and case report form (CRF). This version of the plan has been developed using the protocol (amendment 5 integrated) dated 18 Sep 2017. The final approval of the SAP by Aerpio Therapeutic, Inc. and Trial Runners will occur prior to database lock.

### 1.1 Change from Protocol

Not applicable.

## 2 STUDY OBJECTIVES

The primary objective is to assess the effects of AKB-9778 15 mg once daily (QD) or 15 mg twice daily (BID) for 48 weeks on severity of diabetic retinopathy (DR) in subjects with moderate to severe non-proliferative DR (NPDR).

Secondary objectives include:

- To assess the safety and tolerability of AKB-9778 15 mg QD or 15 mg BID for 48 weeks in subjects with moderate to severe NPDR.
- To determine the AKB-9778 systemic exposure based on sparse Pharmacokinetic (PK) sampling in subjects with NPDR.

## 3 STUDY DESIGNS

This is a Phase 2 randomized, double-masked, placebo controlled, multi-center study, to evaluate the safety and efficacy of 48 weeks of subcutaneous AKB-9778 administered 15 mg QD or 15 mg BID in subjects with moderate to severe NPDR. Exploratory evaluations include pharmacokinetic assessments, as well as exploratory efficacy assessments (OCT-Angiography (OCT-A), Ultra Wide-Field (UWF) imaging and non-invasive Electroretinography (ERG) at a subset of sites. Blood samples will be retained for biomarker and genetic analysis.

Subjects will participate in the study for approximately 56 weeks (screening period up to 4 weeks, baseline and treatment periods for 48 weeks, and follow-up period for 4 weeks). The study will be conducted at approximately 50 investigative sites. Subjects will be randomized 1:1:1 to either AKB-9778 15mg QD, AKB-9778 15mg BID, or placebo treatment groups. Fifty (50) subjects are planned per group. The treatment groups are as follows:

- Active Group: SC AKB-9778 15 mg (QD); To maintain masking, subjects will receive BID dosing with masked study medication administered as one dose of active and one dose of matching placebo.
- Active Group: SC AKB-9778 15 mg (BID)
- Placebo Group: SC phosphate-Buffered-Saline (PBS) (BID)

Subjects will self-administer study medication as subcutaneous (SC) injections in the abdomen (preferably) around the same time every morning and evening, if possible. The investigator, all study-site personnel, all Sponsor personnel (except for an unmasked CMC representative), Central Image Reading Center personnel, and subjects will be masked to treatment assignment during the entirety of the study. Randomization will be stratified by screening Early Treatment of Diabetic Retinopathy Study (ETDRS) Diabetic Retinopathy Severity Score (DRSS) (levels 4, 5 and 6 equally distributed among the treatment groups).

Spot UACR and eGFR will be assessed at baseline, and thereafter every 12 weeks as exploratory assessments to evaluate for any potential effects on renal function. Plasma samples will be collected at specified times on Day 1 and Month 6 visit for PK assessments. These samples will be analyzed for AKB-9778 using validated bioanalytical methods.

A blood sample will be retained for exploratory genetic analysis that may provide insight into the role of the VE-PTP/Tie2 pathway in diabetic retinopathy and an individual subject's response to AKB-9778 treatment. Similarly, blood samples collected at baseline and week 48 End of Treatment (EOT) will be retained for exploratory analysis of biomarkers in plasma associated with VE-PTP inhibition and Tie2 activation. Once results of the study are known, the Sponsor will determine the value of conducting the genetic and biomarker assessments.

### **3.1 Sample Size Considerations**

Estimates for sample size calculations are derived from published data from the analysis of the effect of ranibizumab (Lucentis®) and aflibercept (Eylea®) intravitreal administration regimens on DR severity score in the RISE/RIDE studies and VIVID/VISTA studies, respectively, in which at least 28-46% of subjects improved by  $\geq 2$  steps after 12 months of treatment.

With 45 evaluable subjects per treatment group, the study has  $>85\%$  power (based on Fisher's Exact Test and a 2-sided alpha =0.05) to demonstrate a statistically significant improvement in percent of subjects improving by  $\geq 2$  steps on the ETDRS diabetic retinopathy severity scale, assuming underlying rates for active and placebo of 30% and 5%, respectively. Assuming 10% drop-out/nonevaluable rate, a sample size of 50 subjects per treatment arm (approximately 150 total) was selected.

### **3.2 Randomization**

Approximately 150 subjects will be enrolled in the study. Subjects meeting all eligibility criteria will be randomized 1:1:1 to either AKB-9778 15 mg QD, AKB-9778 15 mg BID, or placebo treatment groups. Fifty (50) subjects are planned per group. The treatment groups are as follows:

- Active Group: SC AKB-9778 15 mg (QD)
- Active Group: SC AKB-9778 15 mg (BID)
- Placebo Group: SC PBS (BID)

Using a central IWRS randomization system, eligible subjects will be assigned in a double-masked fashion 1:1:1 to one of the 3 treatment groups. To maintain balance between treatment groups with respect to DR severity, randomization will be stratified by screening ETDRS DRSS (levels 4, 5 and 6).

### **3.3 Schedule of Evaluations and Analysis Visit Windows**

The schedule of visits and procedures are provided in the protocol. The study consists of 48 weeks of study treatment with 4 week of follow-up period. There is a screening visit (Day-28 to -1), baseline visit (Day 1), site visits at every 4 weeks and follow-up/exit visit at week 52. Tables 1-4 show the visit windows to be used for analyses:

**Table 1: Visit Windows (Data Collected at All Monthly Visits – BP/HR, BCVA, chemistry)**

Visit	Target Day of the Visit	Visit Window (Days) for Analyses
Baseline	1	$\leq 1$
Week 4	29	15-42
Week 8	57	43-70
Week 12	85	71-98
Week 16	113	99-126
Week 20	141	127-154
Week 24	169	155-182

Week 28	197	183-210
Week 32	225	211-238
Week 36	253	239-266
Week 40	281	267-294
Week 44	309	295-322
Week 48	337	323-350

Note: All days are referenced to Day 1

**Table 2: Visit Windows (Data Collected at Months 3, 6, 9, 12 – Body System Assessments, Slit Lamp, IOP, Indirect Ophth, SD OCT, FP, OCT Angiography, ERG, Urinalysis, Fecal Occult Blood Test)**

Visit	Target Day of the Visit	Visit Window (Days) for Analyses
Baseline	1	< = 1
Week 12	85	82-126
Week 24	169	127-210
Week 36	253	211-294
Week 48	337	295-378

Note: All days are referenced to Day 1

Note: Urinalysis was not collected at Week 12, so it should not have a Week 12 Window; all other visit windows are as shown in the table.

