11.7 Efficacy Analyses

All efficacy endpoints are listed in [Sections 5.5](#) and [5.6](#). All efficacy data will be summarized by treatment group and time point using appropriate descriptive statistics. Summaries will be presented for both the MITT and PP populations. Due to the small number of subjects that are expected to be enrolled at each center, all summaries and analyses will be performed using data pooled across centers.

The primary hypotheses to be tested is that AKB-9778 15mg twice daily and AKB-9778 15mg once daily will be superior to placebo in the improvement of DR as measured by the ETDRS severity scale change from baseline at 12 months. Specifically, the primary endpoint is the

percentage of subjects with an improvement in study eye severity of DR (ETDRS DR Severity Score or DRSS) of ≥ 2 steps at Month 12 without need for treatment of PDR or DME (by IVT, laser, or vitrectomy) in the study eye. The primary hypotheses will be tested in the MITT population using a Fisher's Exact Test with a 2-sided 5% significance level. To adjust for multiplicity, a pre-specified testing order will be used. AKB-9778 15mg twice daily will be tested first, and AKB-9778 15mg once daily will be tested second. Details of how missing data will be handled for the primary endpoint, along with sensitivity analyses to assess the impact of missing data will be outlined in the statistical analysis plan (SAP).

Secondary and exploratory endpoints will be analyzed without adjustment for multiplicity, and all inferential analyses will use a 2-sided 5% significance level. Continuous variables will be analyzed using ANCOVA models and/or repeated measures mixed effect models and dichotomous variables will be analyzed using the same approach as outlined for the primary endpoint. Details of how missing data will be handled for secondary and exploratory endpoints will be provided in the SAP.

Exploratory analyses will be conducted to understand the relationship between exposure and response and details of these analyses will be outlined in the SAP.

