### 7.1 Missing Data

Efficacy data related to eye anatomy or visual function that is collected after rescue treatment (i.e., treatment for DME or PDR other than study medication) will be treated as missing data. Unless, otherwise stated, missing data will be handled using the following approach:

- For start date, partial dates will have first day of the month imputed if day is missing, and January of that year will be imputed if month is missing. If both day and month are missing, January 01 will be imputed.
- For end date, partial dates will have last day of the month imputed if day is missing, and December of that year will be imputed if month is missing. If both day and month are missing, December 31 will be imputed.
- Missing data are imputed using Last Observation Carried Forward (LOCF) for all visits except screening/baseline; screening/baseline values are not carried forward.
- For vision related efficacy measurements (Tables 14.2.1.x, 14.2.2.x, 14.2.3.x, 14.2.4.x, 14.2.5.x, 14.2.6.x, 14.2.7.x, 14.2.8.x, 14.2.10.x, 24.2.11.x, 14.2.12.x, 14.2.13, 14.3.12.3, 14.3.13.3, 14.3.14.2x, 14.3.14.5) subjects receiving rescue treatment will be handled differently to reflect their status as a treatment failure and to avoid confounding of the effects of rescue treatment with the effects of study drug. Specifically, last pre-rescue data are carried forward for LOCF analysis. If rescue and DRSS occur on the same day, DRSS from that day is carried forward. For Observed Case (OC) analyses, results post-rescue are omitted, and last pre-rescue data are carried forward. Note that for DRSS scales involving both eyes (Person and Binocular scale) the carry forward rules apply only to the rescued eye in calculation of the combined score.
- Where severity or relationship is missing for adverse events, most conservative imputation will be made.

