### 7.2 Descriptive Statistics

For continuous variables, descriptive statistics will include the number of subjects (n), mean, standard deviation (SD), median, minimum and maximum. Categorical variables will be summarized using absolute and relative frequencies (i.e., counts and percentages). For categorical analyses, eyes that receive rescue therapy will be considered as treatment failures. Safety and PK data will be analyzed as collected.

All efficacy data will be summarized by treatment groups and overall using appropriate descriptive statistics. Summaries will be presented for both the MITT and PP populations, where applicable. Due to the small number of subjects enrolled at each center, all summaries and analyses will be performed using data pooled across centers. Unscheduled data, such as information from unscheduled visits or investigator comments, will be included in the data listings. In general, these data will be excluded from the summary tables unless otherwise specified.

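### The Week 12 window for fundus photographs in SAP Table 2 opens at Day 82, out of line with every other window, and can leave a non-rescued early withdrawal with no DRSS in the primary analysis

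*SAP*

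**What the plan says.** - **Windows.** SAP 3.3 says that "Tables 1-4 show the visit windows to be used for analyses". Table 2 covers, among others, "Slit Lamp, IOP, Indirect Ophth, SD OCT, FP, OCT Angiography, ERG". Its post-baseline rows are Week 12, Days 82-126; Week 24, Days 127-210; Week 36, Days 211-294; Week 48, Days 295-378. The note to the table removes urinalysis from Week 12 and continues "so it should not have a Week 12 Window; all other visit windows are as shown in the table". BCVA is windowed by Table 1 ("Data Collected at All Monthly Visits"), where Week 12 is Days 71-98. SAP 7.3 also assigns recorded data to windows.
- **Missing data.** Protocol 11.7 leaves to the SAP "Details of how missing data will be handled for the primary endpoint, along with sensitivity analyses to assess the impact of missing data". SAP 7.1 gives the general rule: "Missing data are imputed using Last Observation Carried Forward (LOCF) for all visits except screening/baseline; screening/baseline values are not carried forward". SAP 10.1 repeats it for the primary endpoint. For rescued eyes only, SAP 7.1 names the value to carry: "Specifically, last pre-rescue data are carried forward for LOCF analysis". For rescued eyes only, SAP 7.2 names an outcome: "For categorical analyses, eyes that receive rescue therapy will be considered as treatment failures".
- **Population.** MITT (SAP 4.2) requires one dose and no post-baseline assessment.
- **Early withdrawal.** Protocol 7.6 asks for the full end-of-treatment assessments, which include fundus photography, as soon as possible after study medication stops. These can fall on any study day.

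**The concern.** One row of one table departs from the pattern of all the others, and it is a row that governs DRSS. A photograph taken a few days early, or at a withdrawal visit in the second or third month, has no analysis visit, while one taken up to 41 days late does. On Days 71-81 a single visit can give a Week 12 BCVA but no Week 12 DRSS.

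The row also bears on the primary endpoint. If the values available for carrying forward are the windowed ones, a collected and gradable photograph from before Day 82 drops out, and baseline cannot replace it. A dosed, non-rescued subject then has no DRSS at Week 48 but remains in MITT. The SAP does not say whether that subject is a non-responder or leaves the denominator. At stake are the Week 12 DRSS summaries and, for a small number of subjects, the primary denominator.

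**Working it through.** **1. The plan's own figure.** Inputs from SAP 3.1: 45 evaluable per arm, 30% vs 5%, Fisher's exact test, two-sided 0.05. Exact enumeration over the two binomials gives power 86.3%, which agrees with the stated >85%. Also 45/(1 - 0.10) = 50 per arm. The sample size is not in question.

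**2. Offsets of each window from its target day (lower/upper limit minus target).**

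| SAP table | Post-baseline rows | Offset |
|---|---|---|
| 1 | all 12 | -14/+13 |
| 2 | Week 12 (target 85) | 82 - 85 = -3; 126 - 85 = +41 |
| 2 | Weeks 24, 36, 48 | -42/+41 |
| 3 | both | -84/+83 |
| 4 | all 6 | -28/+27 |

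Table 2 Week 12 is the only irregular row. On the pattern of its own table it would open at 85 - 42 = Day 43. The irregular gap is Days 43-81, which is 39 days. Uncovered days before the first window are not unusual in themselves (Table 3 leaves Days 2-84 uncovered), so Days 2-42 are not counted as irregular.

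**3. Who is touched.** Protocol 9.3.1 sets Month 3 at 84 ± 3 days from Day 1, which is study Days 82-88. All of these lie inside 82-126. Affected are visits made earlier than the protocol allows and early-withdrawal photographs. BCVA and DRSS disagree on Days 71-81 (11 days).

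**4. Two readings of LOCF for a non-rescued subject whose only post-baseline photograph is on Day 60.**
- Windowed records (suggested by SAP 3.3 and 7.3): Day 60 has no window, nothing is carried, and there is no DRSS at Week 48.
- Last photograph by date (the ordinary sense of last observation): Day 60 is carried to Week 48.

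The other listed runs (SAP 10) do not settle this. The per-protocol population requires the 48-week visit, and the observed-case analysis has no Week 48 record for this subject. On either reading, a dosed, non-rescued subject with no post-baseline photograph at all has no stated outcome.

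**5. How many.** The documents do not give the timing of drop-out. Assumption: 5 per arm (the planned 10% of 50, although that rate also includes non-evaluable subjects), all non-rescued, spread evenly over Days 2-336 (335 days), each with a last photograph at about the day of withdrawal.
- Days 43-81: 5 × 39/335 = 0.58 per arm.
- Days 2-81: 5 × 80/335 = 1.19 per arm.
- Range: 0 to 5 per arm.

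**6. Effect on the primary test (two-sided Fisher, illustrative counts).**

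| Active | Placebo | p |
|---|---|---|
| 10/50 | 3/50 | 0.071 |
| 10/49 (one active non-responder excluded) | 3/50 | 0.041 |
| 10/49 | 3/49 (one excluded in each arm) | 0.071 |

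Exact enumeration from 50 per arm gives the probability that excluding exactly one active non-responder, and nobody on placebo, turns p ≥ 0.05 into p < 0.05. It is 3.8% at true rates of 30% vs 5% and 10.7% at 20% vs 5%. If one non-responder is excluded in each arm, or one on placebo only, the probability is essentially zero.

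**The case against.** The strongest defence has four parts.

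- **Day 82 may be deliberate.** It is the first day on which the protocol permits a Month 3 visit, and no photograph is scheduled between screening and then. A reader might infer that Week 12 data are being lost generally. They are not, since every on-schedule photograph is captured. Still, no other lower limit in Tables 1-4 uses the ±3-day tolerance, nor does this row's own upper limit, and the SAP gives no reason.
- **Last observation has a plain meaning.** The SAP excludes only screening and baseline values from being carried, and nowhere says that a photograph outside a window is discarded. A reader might infer that early-withdrawal photographs will certainly be dropped. The documents do not support that; it is one of two available readings. Nor does stopping treatment before Day 82 by itself mean no windowed photograph, because the end-of-treatment assessment follows the stop and may fall on or after Day 82.
- **The effect needs one-sided loss.** This stands. Nothing in the documents predicts that losses would fall only in an active arm, so 3.8% and 10.7% are conditional figures and not the chance that the gap changes the result.
- **There are safeguards.** The SAP is to be approved before database lock (SAP 1), populations are set before analysis (SAP 6), and derived datasets must match between two programmers (SAP 15). A reader might infer that the rule would be chosen with treatment codes in hand, because SAP 6 places the analyses after unmasking. The documents do not show this. Double programming would expose a disagreement, but it supplies no rule for resolving it.

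**Conclusion.** The point holds in limited form. The Table 2 Week 12 row is irregular and unexplained. Followed as written with windowed LOCF, it discards collected photographs and can leave a dosed, non-rescued subject without a DRSS in the primary analysis. The missing LOCF source and the missing counting rule would alone be largely matters of detail; the window gives them a practical consequence.

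The expected size is small: about 0.6 subjects per arm in Days 43-81 under the stated drop-out assumptions, with a range of 0 to 5. The stated power stands. The primary conclusion could move only if the result lay near 0.05 and the loss fell on an active arm alone; a balanced loss leaves p at 0.071 in the example. Rescued study eyes are outside this point, because the SAP already classes them as failures. Severity is minor to should-fix.

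**What to change.** 1. **SAP Table 2.** Change the Week 12 window to Days 43-126 for the assessments actually collected at Month 3, or state that Day 82 is deliberate and why. Neither urinalysis nor fecal occult blood should have a Week 12 window. The note already removes urinalysis; fecal occult blood is listed in Table 2 although the protocol schedule does not collect it at Month 3.
2. **SAP 7.1.** Add that, where an analysis visit has no DRSS of its own, LOCF uses the latest gradable post-baseline photograph taken on or before the end of that visit's window, including Early Withdrawal/EOT photographs, and that the existing pre-rescue and same-day rescue rules are unchanged. The cut-off at the end of the window matters because DRSS is also analysed at Weeks 12, 24 and 36; without it, later photographs could be carried backward.
3. **SAP 10.1.** Add that MITT subjects with no post-baseline DRSS stay in the primary denominator as non-responders. The downside is slightly conservative response rates.

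Item 1 serves the Week 12 analyses; items 2 and 3 settle the primary endpoint. The cost is one table cell with its note, two sentences and minor programming before unmasking. No new data are needed.

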**Table 3: Visit Windows (Data Collected at Months 6 and 12 – Height, Weight, Temperature, FA)**

Visit	Target Day of the Visit	Visit Window (Days) for Analyses
Baseline	1	< = 1
Week 24	169	85-252
Week 48	337	253-420

Note: All days are referenced to Day 1

**Table 4: Visit Windows (Data Collected at Months 2, 4, 6, 8, 10, 12 – Hematology)**

Visit	Target Day of the Visit	Visit Window (Days) for Analyses
Baseline	1	<= 1
Week 8	57	29-84
Week 16	113	85-140
Week 24	169	141-196
Week 32	225	197-252
Week 40	281	253-308
Week 48	337	309-364

Note: All days are referenced to Day 1

When multiple observations are captured in a visit window, use the scheduled visit that matches the visit window in the analysis (e.g., if week 24 scheduled visit is in the week 24 window, use this visit for Week 24 analysis visit). If there is no scheduled visit that matches the visit window, the one closest to the target date of the visit will be used to represent the window. If two observations are equidistant from the target date, then the observation that is closer to the upper end of the window visit will be used.

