9.3 Schedule of Activities

The Schedule of Activities is presented in [Appendix A](#) and shows the timing of planned study procedures to be conducted at the study site and at the home care nursing visits. Every effort should be made to adhere to the procedure schedule and all assessments should be completed at each study visit.

The Screening, Baseline, Treatment, and Follow-up Periods will require subject participation for approximately 56 weeks.

Study procedures, clinical assessments (including laboratory assays), and PK, biomarker and genetic sampling will be performed as indicated in the Schedule of Activities.

Subjects will be responsible for self-administration of study medication which is provided in prefilled sterile syringes. The subject will self-inject BID on a morning and evening schedule as detailed in [Section 8.3.5](#). Subjects will dose BID with the exception of Day 1 when the subject will dose the first (AM) dose at the clinic and will begin the BID dosing schedule on Day 2. No PM dose will be taken on Day 1.

At the visit on Day 1, the site will train the subject on SC study medication administration and dosing diary completion. After the pre-dose activities have been completed, the subject will self-administer the AM dose of study medication.

After the subject has completed the EOT visit, no further subcutaneous dosing will occur.

Study visits on Day 1, Month 6 and Month 12 EOT should be scheduled for the morning. The remainder of the site visits should also be scheduled for the morning when possible. Subjects will maintain a daily study medication diary and will record timing and location of dose.

At the site visits on Day 1 and Months 1 through 11, subjects will be dispensed subcutaneous study medication and dosing supplies.

Subjects discontinuing study medication sooner than the planned 12-month dosing period or withdrawing from the study should complete the Month 12 EOT assessments including the EOT assessments at the EOT site visit (See [Section 9.3.2.16](#)) and the EOT homecare nurse visit (See [Section 9.3.3.5](#)).

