9.3.1 Visit Windows

Plasma PK samples collected at 30 and 90 minutes after dosing of study medication on Day 1 and Month 6 should be collected within ± 10 minutes of the target time. If for any reason, the sampling time point for a given sample falls outside of the visit window, the sample must still be collected. For all samples; the exact time of sample collection will be recorded.

Blood pressure and heart rate evaluations performed must be conducted within ± 20 minutes of the designated time.

Subjects will only use AM syringes for dose administration in the morning and PM syringes for dose administration in the evening. Subjects should administer their daily doses around the same time every morning and evening, if possible. If a dose is missed, this dose should be skipped and the subject should maintain the morning and evening dosing schedule.

The Day 7 phone call must be conducted within ± 3 days.

Site visits scheduled for Months 1 through 12 should be conducted within 28 days times the study month number ± 3 days relative to the baseline visit (e.g. Month 1 visit window is 28 ± 3 days from Day 1, Month 2 visit window is 56 ± 3 days from Day 1, etc.).

Homecare nurse visits scheduled for Screening, Months 3, 6, 9 and 12 should be conducted within 1 week after the corresponding site visit. The Follow-up homecare visit occurs 4 weeks ± 3 days after the EOT visit at the site.

The fecal occult blood specimen collection and shipping to the Central Laboratory should be conducted by the subject within the week following the corresponding site visit.

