11.5 Study Days and Assessment Windows

Study days will be numbered relative to the first day of dosing. The start of study (Day 1) will be defined as the date on which a subject takes the first dose of any study medication, as recorded on the CRF. Relative to study start, days will be numbered ...-2, -1, 1, 2, ... with Day -1 being the day prior to the start of study medication (Pre-Dose).

Recorded data will be assigned to evaluation/assessment windows. If more than one clinical evaluation is made within a window for a particular visit, the record with the worst assessment will be used for the assessment in that window.

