### 5.5 Safety Endpoints

Safety endpoints include:

- Incidence and severity of systemic and ocular AEs
- Ocular AEs at Study eyes, all qualified eyes and unqualified fellow eyes during treatment period.
- Shift from baseline in body system assessments for the parameters general appearance, HEENT (Head, Ears, Eyes, Nose and Throat), cardiovascular, respiratory, abdomen/gastrointestinal, musculoskeletal, and dermatologic at week 12, 24, 36, 48.
- Change from baseline in vital sign measurements (SBP, DBP, HR, BMI, Weight and Temperature) at every 4 weeks.
- Change from baseline in ECG parameters (HR, PR, QRS and QTcF) at week 24, 48.
- Change from baseline in clinical laboratory assay results (blood chemistry (at every 4 weeks), hematology (at every 8 weeks), fecal occult blood test (at week 24, 36, 48), and urinalysis (at week 24, 36, 48).
- Mean change from baseline in ETDRS Best Corrected Visual Acuity (BCVA) letter score in the study eyes, all qualified eyes and unqualified fellow eyes at every 4 weeks.
- Proportion of subjects with a loss of ≥15 letters, loss of ≥10 letters and loss of ≥5 letters in BCVA compared to baseline at week 48.
- Mean change from baseline in Spectral Domain Optical Coherence Tomography (SD OCT): Central Subfield Thickness (CST) in the study eyes, all qualified eyes and unqualified fellow eyes at week 12, 24, 36, 48.

- Proportion of subjects with increase of  $\geq 100$   $\mu\text{m}$  and increase of  $\geq 50$   $\mu\text{m}$  SD OCT: CST in the study eyes, all qualified eyes and unqualified fellow eyes at week 48.
- Change from baseline in Intraocular Pressure (IOP), with additional sub-group analysis with baseline IOP  $< 16$  mmHg and baseline IOP  $\geq 16$  mmHg in the study eyes and fellow eyes at week 12, 24, 36, 48.
- Shift from baseline in Slit Lamp Biomicroscopy examination for the parameters Eyelids, Cornea, Conjunctiva, Anterior Chamber, Iris/Pupil and Lens in all qualified eyes and unqualified fellow eyes at week 12, 24, 36, 48.
- Shift from baseline in Dilated Indirect Ophthalmoscopy examination for the parameters Vitreous, Macula, Optic Nerve, and Peripheral Retina in all qualified eyes and unqualified fellow eyes at week 12, 24, 36 and 48.

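### SAP 3.3 tabulates the scheduled or nearest skin exam in a window where the protocol requires the worst, so an early stopper's end-of-treatment exam can go untabulated

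*SAP*

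**What the plan says.** Protocol 11.5 (Study Days and Assessment Windows) covers the case of more than one clinical evaluation in a window: "the record with the worst assessment will be used for the assessment in that window". Body system assessments, including direct observation of the skin, are among the clinical evaluations in Protocol 9.2.1.

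SAP 3.3, in the text after Table 4, sets a different rule: "When multiple observations are captured in a visit window, use the scheduled visit that matches the visit window in the analysis". Failing that, "If there is no scheduled visit that matches the visit window, the one closest to the target date of the visit will be used", and a tie goes to the later observation. SAP Table 2 applies its windows to "Body System Assessments, Slit Lamp, IOP, Indirect Ophth, SD OCT, FP, OCT Angiography, ERG, Urinalysis, Fecal Occult Blood Test". SAP 5.5 lists the shift from baseline in body systems, ending "musculoskeletal, and dermatologic at week 12, 24, 36, 48". SAP 1.1 (Change from Protocol) reads "Not applicable".

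Two visit rules matter. Protocol 9.3 says: "Subjects discontinuing study medication sooner than the planned 12-month dosing period or withdrawing from the study should complete the Month 12 EOT assessments". This includes the EOT nurse visit, which is due within a week of the EOT site visit. Protocol 9.3.1 adds: "The Follow-up homecare visit occurs 4 weeks ± 3 days after the EOT visit at the site". The follow-up visit repeats the body system exam, and dosing has ended by then.

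**The concern.** The two documents give different rules for the same table, and the SAP does not disclose the difference. The consequence falls on subjects who stop early. They have an EOT exam soon after the last dose and a second exam about four weeks later. Nothing in SAP 3.3 or Table 2 confines the treatment-week rows to on-treatment exams, so the later exam can be the one reported.

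The skin exam matters for this drug. In the 9-month dog study dermal nodules appeared during dosing and resolved quickly once dosing stopped (Protocol 4.2). Protocol 4.4.1 leaves open whether ectasias will occur in patients dosed for more than 3 months. Change from baseline in body system assessments is a listed safety endpoint. A rule that can prefer an off-drug exam to the EOT exam is therefore not neutral in direction, and the shift table could disagree with the adverse event tables only because of how records were selected.

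**Working it through.** **Windows.** Table 2 targets are Days 85, 169, 253 and 337. Midpoints between targets reproduce Week 24 (127–210), Week 36 (211–294) and Week 48 (295–378). Week 12 is printed as 82–126; its lower bound does not follow the midpoint rule, which would give Day 43. The printed windows are used below.

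**Assumptions.** Site visits fall on target and each nurse exam is 3 days later (the protocol allows 0 to 7). Follow-up is 28 days after the EOT site visit (the protocol allows ±3). With stop day s = EOT site visit:

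- EOT exam: e = s + 3
- follow-up exam: f = s + 28
- scheduled nurse exams: Days 88, 172 and 256, if the site visit (85, 169, 253) came before s

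The Month 12 site visit may fall as early as Day 334, so early stopping means s ≤ 333. The EOT exam lies in a Table 2 window when s + 3 ≥ 82, so s = 79 to 333, which is 255 days.

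**Loss to an earlier scheduled exam.** If that window's scheduled exam has already taken place, it is chosen whatever the distances. This occurs for s = 86–123, 170–207 and 254–291: 3 × 38 = 114 days.

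**Replacement by follow-up in the same window.** With no scheduled exam in the window, follow-up wins when |s + 28 − T| ≤ |s + 3 − T|, that is, s ≤ T − 15.5.

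- Week 24 (T = 169): s = 124–153, 30 days
- Week 36 (T = 253): s = 208–237, 30 days
- Week 48 (T = 337): s = 292–321, 30 days
- Week 12 (T = 85): would need s ≤ 69, but the window starts at s = 79, so none

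The total is 90 days. With a nurse lag of 0 or 7 days, the count per window is 29 or 32 instead of 30.

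**EOT exam used.** s = 79–85, 154–169, 238–253 and 322–333: 7 + 16 + 16 + 12 = 51 days. Check: 51 + 90 + 114 = 255.

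| Outcome for the EOT exam | Stop days | Share of 255 |
|---|---|---|
| Used | 51 | 20% |
| Replaced by follow-up, same window | 90 | 35% |
| Loses to earlier scheduled exam | 114 | 45% |
| Unused in total | 204 | 80% |

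**Example.** For s = 140 the EOT exam is on Day 143, 26 days from target 169. Follow-up is on Day 168, 1 day from target. The SAP reports follow-up as Week 24; the protocol rule takes the worse of the two.

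**Visit coding.** If the early-withdrawal visit is coded as the scheduled Week 48 visit, the 30 Week 48 days drop out. Replacement is then 60 of 255 (24%) and total unused is 174 (68%).

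**Subjects per arm.** The planned 10% drop-out gives 0.10 × 50 = 5. Stop days are spread evenly over Days 2–333 (332 days):

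- replaced by follow-up: 5 × 90/332 = 1.4, or 5 × 60/332 = 0.9 with the alternative coding
- lost to an earlier scheduled exam: 5 × 114/332 = 1.7

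**Completers.** The EOT nurse exam falls on Days 334–347 and follow-up on Days 359–371. Both are in the Week 48 window, but the scheduled Week 48 exam is chosen, and it is also always the nearer one.

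**The case against.** The strongest reply is that little is lost. A subject who stops because of a skin lesion should have an adverse event recorded, and so would appear in the TEAE tables, the presentation of events leading to discontinuation and the listings. Nurses pass possible events to the investigator. This stands and is why the point is minor. It is not full cover, because it depends on the investigator judging the finding to be an event.

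Second, the SAP may intend follow-up to stay outside the windows. SAP 3.3 names a separate exit visit at week 52, and SAP 5.5 limits the shift to Weeks 12 to 48. On that reading replacement by follow-up disappears, but the SAP does not say so, and the 114 days of loss to an earlier on-treatment exam remain.

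Third, the per-arm figures lean high. The 10% covers non-evaluable subjects as well as drop-outs, and subjects who withdraw consent do not enter follow-up. The dog finding has no stated resolution time, and no unusual skin findings were seen in patients treated for up to 3 months.

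Two stronger readings are tempting but unsupported. A reader might count 165 stop days as replacement, because on 75 further days (s = 99–123, 183–207, 267–291) the follow-up exam fills a later treatment-week row. On those days it lies in a different window from the EOT exam, which has already lost to an on-treatment exam. The off-drug exam is mislabelled there, but it displaces nothing, and the protocol rule applied to the same windows would place it in the same row. A reader might also say that completers lose their last skin exam. Their Week 48 row correctly shows the Week 48 exam; that follow-up has no row of its own is a reporting gap, not a selection error.

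**Conclusion.** The concern holds as a minor point. The conflict between Protocol 11.5 and SAP 3.3, undeclared in SAP 1.1, needs no assumptions. Its effect is confined to early discontinuers and is small: about 1 subject per arm (0.9 to 1.4) whose EOT exam is replaced by follow-up, and about 1.7 who lose it to an earlier scheduled exam. These figures assume that all of the 10% drop-out are early stoppers, that stop days are evenly spread, that all attend follow-up, and that visits follow the timing above. Fewer cells than that would change, since the EOT exam must be abnormal and the exam kept must not be. The documents give no rate for that combination, so none is assumed.

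It would be wrong to infer that the safety analysis as a whole would miss a skin signal: findings reported as adverse events are still counted and listed.

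**What to change.** In SAP 3.3, for the body system shift tables and the other Table 2 safety shifts:

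- Use the Protocol 11.5 worst-record rule among on-treatment exams in the window.
- State that the EOT or early-withdrawal exam counts as on-treatment, although the nurse visit may fall a few days after the last dose.
- Keep follow-up exams out of the Week 12 to Week 48 rows and tabulate them separately as Week 52.
- Record any remaining departure from the protocol in SAP 1.1.

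The on-treatment restriction goes beyond the protocol text, but it is needed. Applied literally to Table 2, the worst-record rule would bring completers' off-drug follow-up exam into Week 48.

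The cost is SAP wording and a small programming change, with no new visits or data. The downside is a slightly higher abnormal rate in every arm, because more exams per subject count. The change does not recover EOT exams before Day 82 (stop days 2 to 78 under the timing above), which fall in no Table 2 window under either rule.
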